### 9.3.5. Other Safety Analyses

All safety analyses will be performed on the Safety Analysis Set.

AEs, ECGs and safety laboratory data will be reviewed and summarized on an ongoing basis during the study to evaluate the safety of participants. Any clinical laboratory, ECG and PR abnormalities of potential clinical concern will be described. Safety data will be presented in tabular and/or graphical format and summarized descriptively, where appropriate.

Medical history and physical examination and neurological examination information, as applicable, collected during the course of the study will be considered source data and will not be required to be reported, unless otherwise noted. However, any untoward findings identified on physical and/or neurological examinations conducted during the active collection period will be captured as AEs, if those findings meet the definition of an AE. Data collected at screening that are used for inclusion/exclusion criteria, such as laboratory data, ECGs, and vital signs, will be considered source data, and will not be required to be reported, unless otherwise noted. Demographic data collected at screening will be reported.

#### 9.3.5.1. Electrocardiogram Analyses

Changes from baseline for the ECG parameters QT interval, heart rate, QTcF interval, PR interval, and QRS complex will be summarized by treatment and time.

The number (%) of participants with maximum postdose QTcF values and maximum increases from baseline in the following categories will be tabulated by treatment:

#### Safety QTcF Assessment

Degree of Prolongation	Mild (msec)	Moderate (msec)	Severe (msec)
Absolute value	<450-480	>480-500	>500
Increase from baseline		30-60	>60

In addition, the number of participants with uncorrected QT values >500 msec will be summarized.

#### 9.3.5.2. Adverse Events

AEs (except CRS and ICANS) will be graded by the investigator according to NCI CTCAE version 5.0 and coded using Med.ORA. CRS and ICANS will be assessed according to ASTCT criteria (See [Appendix 12](#)) and coded using Med.ORA. AEs will be characterized by type, frequency, severity, timing, seriousness, and relationship to ehanatamab. AEs will be presented with and without regard to causality based on the investigator's judgment. The frequency of overall toxicity, categorized by toxicity Grades 1 through 5, will be described. Additional summaries will be provided for AEs that are observed with higher frequency and for AEs identified in Section 8.3.8, including CRS and ICANS.

#### 9.3.5.3. Laboratory Test Abnormalities

Clinical laboratory data will be classified by grade according to NCI CTCAE version 5.0 and will be analyzed using summary statistics. The worst on-treatment grades during the treatment period will be summarized. Shifts in toxicity grading from baseline to highest grade during the on-treatment period will be displayed. Results for laboratory tests that are not part of NCI CTCAE will be presented as below, within, or above normal limits. Only participants with post-baseline laboratory values will be included in these analyses. Further details of analyses for all the laboratory parameters will be provided in the SAP.

CCI

### 9.4. Interim Analyses

#### 9.4.1. Interim Safety Assessments

Interim safety assessments will be performed on this study and will be performed on Part 1 and 2 combined.

An internal safety review team will review cumulative safety data during the study conduct (see Section 10.1.5.1). In addition, the incidence of the following events will each be monitored by the Sponsor throughout the study. The review results and decisions will be documented in the study TMF.

- Grade 3-4 CRS;
- Grade 3-4 ICANS;
- Grade 4 treatment-related non-hematologic events (excluding CRS and ICANS);
- Grade 3-4 treatment-related GBS/GB-like AEs;
- Grade 4 treatment-related sensory neuropathy/other IR neurologic AEs (excluding ICANS)
- Grade 3-4 treatment-related motor neuropathy
- Grade 5 events.

If the number of participants observed to have such identified events exceeds a prespecified threshold, the study will be placed on a temporary enrollment hold by the sponsor. During any temporary enrollment hold, no new participants can be enrolled, nor can any newly enrolled participants start study intervention. Participants who have already started study intervention may continue treatment only if the benefit/risk assessment for the participant is judged to be positive by the investigator in consultation with the sponsor. In the event that any criteria for the temporary enrollment hold are met, written notification documenting the reason for the temporary hold and/or termination will be provided by the sponsor to the investigators, the EC/IRBs, the regulatory authorities, and any CRO(s) used in the study.

The criteria for placing the study on temporary hold for the following safety reasons are based on Bayesian posterior probabilities. Using a non-informative Beta (0.5, 0.5) prior distribution, if the number of participants observed to have Grade 3 or 4 CRS results in a  $\geq 0.80$  posterior probability that the true Grade 3 or 4 CRS rate exceeds 20%, the study will be put on a temporary hold. Separate but similar criteria will be used for participants with Grade 3-4 ICANS and treatment-related Grade 4 non-hematologic events (excluding CRS and ICANS). Table 9 summarizes the minimum number of participants with such identified events that would meet the above criteria.

**Table 9. Minimum Number of Participants With Identified Events That Would Prompt Temporary Enrollment Hold (CRS, ICANS, Non-hematologic treatment-related AEs)**

Number of Evaluable Participants	10-13	14-18	19-22	23-26	27-30	31-35	36-39
Minimum number of participants with Grade 3-4 CRS events that would lead to a temporary enrollment hold*	4	5	6	7	8	9	10

**Table 9. Minimum Number of Participants With Identified Events That Would Prompt Temporary Enrollment Hold (CRS, ICANS, Non-hematologic treatment-related AEs)**

Number of Evaluable Participants	10-13	14-18	19-22	23-26	27-30	31-35	36-39
Minimum number of participants with Grade 3-4 ICANS events that would lead to a temporary enrollment hold*	4	5	6	7	8	9	10
Minimum number of participants with Grade 4 treatment-related non-hematologic events (excluding CRS and ICANS) that would lead to a temporary enrollment hold*	4	5	6	7	8	9	10

Prior distribution: Beta (0.5,0.5)

Criteria for 40 or more evaluable participants will be calculated such that the study will be put on temporary hold if the posterior probability that the true event rate exceeds 20% is greater than or equal to 0.80.

Evaluable participants are defined as those who have received at least 1 dose of study treatment having an identified event or those without such an event who have been followed for at least 28 days from first dose.

\* The study will be put on temporary hold as soon as the minimum number of evaluable participants with the identified AEs has reached the threshold (eg, if there are 4 participants experiencing the identified AE out of the first 6 evaluable participants, the study will be put on hold). A minimum of 4 events are required to trigger a temporary hold.

The criteria for placing the study on temporary hold for the following safety reasons are based on Bayesian posterior probabilities using a non-informative Beta (0.5, 0.5) prior distribution. Specifically,

- if the number of evaluable participants observed to have treatment-related Grade 3-4 GBS/GB-like AEs results in a posterior probability that the true rate of such events exceeding 3% is  $\geq 0.80$ , the study will be put on a temporary hold;
- if the number of evaluable participants observed to have treatment-related Grade 4 sensory neuropathy/other IR neurologic AEs (excluding ICANS) or treatment-related Grade 3-4 motor neuropathy results in a posterior probability that the true rate of such events exceeding 10% is  $\geq 0.80$ , the study will be put on a temporary hold.

Table 10 summarizes the minimum number of evaluable participants with such identified events that would meet the above criteria.

**Table 10. Minimum Number of Participants With Identified Treatment-Related Events That Would Prompt Temporary Enrollment Hold (GBS/GB-like AEs, Peripheral Neuropathy/IR Neurologic AEs)**

Number of Evaluable Participants	20-39	40-64	65-90	-	-	-	-	-	-
Minimum number of participants with Grade 3-4 treatment-related GBS/GB-like events that would lead to a temporary enrollment hold*	2	3	4	-	-	-	-	-	-
Number of Evaluable Participants	6-11	12-19	20-27	28-35	36-43	44-52	53-60	61-69	70-78
Minimum number of participants with Grade 4 treatment-related sensory neuropathy /IR neurologic AE (excluding ICANS) or Grade 3-4 treatment-related motor neuropathy events that would lead to a temporary enrollment hold**	2	3	4	5	6	7	8	9	10

Prior distribution: Beta (0.5,0.5)

Evaluable participants are defined as those who have received at least 1 dose of study treatment having an identified event or those without such an event who have been followed for at least 28 days from first dose.

\*The study will be put on temporary hold as soon as the minimum number of evaluable participants with the identified AEs has reached the threshold (eg, for GBS/GB-like AEs, if there are 2 participants experiencing the identified AE out of the first 10 evaluable participants, the study will be put on hold). A minimum of 2 events are required to trigger a temporary hold.

\*\* The study will be put on temporary hold as soon as the minimum number of evaluable participants with the identified AEs has reached the threshold (eg, if there are 2 participants experiencing the identified AE out of the first 4 evaluable participants, the study will be put on hold). A minimum of 2 events are required to trigger a temporary hold.

In addition, the study will be put on temporary hold if any of the following criteria are met:

- 1 Grade 5 event of CRS (by ASTCT criteria);
- 1 Grade 5 event of ICANS (by ASTCT criteria);
- 1 Grade 5 treatment-related peripheral neuropathy or IR neurologic event;
- Any 2 treatment-related Grade 5 events (excluding CRS and ICANS and peripheral neuropathy/IR neurologic event).

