### 4.3.2. Justification for Evaluation of Higher Elranatamab Doses

An MTD was not achieved in C1071001, and the safety and efficacy for doses greater than 76 mg has not been established. Increasing the dose of elranatamab may allow for a longer dosing interval and a lower frequency of administration while maintaining the overall exposure (ie, AUC) of total eh-anatamab between 152 mg Q2W similar to 76 mg QW.

Based on the results of the quantitative systems pharmacology simulations, higher eh-anatamab doses with longer dosing intervals (ie, Q2W, Q4W and- are expected to be adequate to maintain the response given the reduced disease burden in these participants. The higher eh-anatamab dose levels explored in Part 2A/Part 2B, specifically Part 2A Dose level 2 of 152 mg Q2W/Q4W which is the target dose level for Part 2A/2B, provide a similar overall dose intensity (AUC) to 76 mg QW/Q2W. Dose level 1 (116 mg) represents ~ 50% increase from 76 mg. Dose level 2 (152 mg) represents ~ 30% increase from 116 mg. CCI

The dosing regimens to be evaluated in Part 2AIB, Part 2C and Part 1 after 6 cycles and after 12 cycles are expected to further saturate the sBCMA sink and result in higher unbound eh-anatamab exposure across the dosing interval. Therefore, these regimens could derive, maintain and/or further deepen clinical responses. In addition, less frequent dosing might provide additional patient convenience and improve compliance.

CCI

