### 9.5.2. Part 2A and Part 2C

In Part 2A and 2C, approximately 8 participants at each dose level will be enrolled and treated to ensure at least 6 DLT evaluable participants (as defined in Section 9.2) to be evaluated. If any participant is deemed non-evaluable for DLT, additional participants may be enrolled to ensure there are a sufficient number of evaluable participants in Part 2A.

A BLRM will be utilized for dose determination in Part 2A as well as dose opening in Part 2C. The dosing decision and estimation of the RP2D of elranatamab will be guided by the estimation of the posterior probability of DLT in the DLT observation period. Other evidence such as safety data beyond DLT window, clinical activity, PK, and PD data will also be evaluated in determining RP2D. After each dosing cohort of participants completes the DLT observation period, the posterior distribution for the risk of DLT for each dose level will be evaluated. The posterior distributions will be summarized to provide the posterior probability that the risk of DLT lies within the following intervals.

- Underdosing: [0, 0.16);
- Target toxicity: [0.16, 0.33);
- Excessive toxicity: [0.33, 1].

Dosing decisions are guided by the EWOC principle.[50] A dose level may only be used for the next dosing cohort of participants if the risk of excessive toxicity ([0.33, 1]) at that dose level is less than 25%.

Table 13 shows some hypothetical dose escalation data scenarios and the corresponding recommendations for the next dose. For example, in Scenario 1, if 1 participant experiences a DLT out of 6 DLT-evaluable participants at 116 mg Q2W dose level, the recommendation is to escalate to the next dose level (152 mg Q2W) with probability of overdosing of 0.083 at 152 mg dose level. In Scenario 3, if 3 participants experience DLTs out of 6 DLT-evaluable participants at 116 mg Q2W dose level, the dose level is deemed too toxic, and the dose finding process will stop with no RP2D identified.

For Part 2C, the dose level to be explored (116 mg QW or 152 mg QW) depends on the toxicity profile observed in Part 2A. For example, if there is 0 DLT in 6 DLT-evaluable participants at both Dose level 1 and Dose level 2 in Part 2A, respectively, then 152 mg QW may be evaluated in Part 2C. However, if there is 1 DLT observed in 6 DLT-evaluable participants at both Dose level 1 and Dose level 2 in Part 2A, respectively, then 116 mg QW may be evaluated in Part 2C.

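### Part 2B has no dose-specific toxicity trigger, and the pooled 20% hold rule has very little power for excess non-fatal toxicity at 152 mg from Cycle 2

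*Protocol*

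**What the plan says.** Protocol 9.4.1 sets the population for all hold rules: "Interim safety assessments will be performed on this study and will be performed on Part 1 and 2 combined". SAP 7.2.1 repeats the rules but not that sentence.

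Three Bayesian limits apply, each with a Beta(0.5, 0.5) prior and a 0.80 cut-off:
- **20%**, separately for Grade 3-4 CRS, Grade 3-4 ICANS and Grade 4 related non-hematologic events. The hold criterion is that the "posterior probability that the true event rate exceeds 20% is greater than or equal to 0.80", with a floor: "A minimum of 4 events are required to trigger a temporary hold".
- **10%**, for related Grade 4 sensory or immune-related neurologic events or Grade 3-4 motor neuropathy, with at least 2 events.
- **3%**, for related Grade 3-4 GBS-like events, with at least 2 events.

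Participants count as evaluable if they have an identified event after at least one dose, or if they are "those without such an event who have been followed for at least 28 days from first dose". The first dose is the 4 mg priming dose in every part.

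The DLT window in Protocol 4.3.3 instead runs 28 days from the first 116 or 152 mg dose. It applies to Parts 2A and 2C, as does the dose model in Protocol 9.5.2: "A BLRM will be utilized for dose determination in Part 2A as well as dose opening in Part 2C". Part 2C will not be explored (Protocol 4.1). On the higher doses, Protocol 4.3.2 says: "An MTD was not achieved in C1071001, and the safety and efficacy for doses greater than 76 mg has not been established".

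**The concern.** Cycle 1 is the same in all parts, so pooling suits Cycle 1 CRS and ICANS. From Cycle 2 the parts diverge: Part 1 stays on 76 mg weekly through Cycle 6, while Part 2 moves to 116 or 152 mg every two weeks. A pooled rate for later toxicity then averages over different regimens. When Part 2B data arrive, the denominator already holds about 30 Part 1 and 8 Dose level 1 participants.

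The clock adds to this. With 28-day cycles, C2D1 is nominally Day 29, so a Part 2 participant can count as event-free with almost no exposure to the higher dose (a few days at most, at the early edge of the ±3-day window).

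At stake is what the absence of a hold means. Part 2B exists to confirm the safety of the selected regimen and the study has no data monitoring committee, so a reader may take silence from these rules as reassurance about 152 mg.

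**Working it through.** **Inputs.** Prior, cut-off, limits and minimum counts are from Protocol 9.4.1. Planned sizes are from Protocol 4.1 and 9.5: Part 1 = 30, Part 2A = 8 per dose level, Part 2B = 22. So 30 + 8 = 38 participants are not at 152 mg, 8 + 22 = 30 are, and 38 + 30 = 68 in all. True event rates are assumptions.

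**Step 1: reproduce the plan's tables.** The threshold at n evaluable is the smallest r with Pr(p > p0 | Beta(0.5 + r, 0.5 + n − r)) ≥ 0.80, subject to the minimum count. For the 20% rule this gives 4/5/6/7/8/9/10 at n = 10-13/14-18/19-22/23-26/27-30/31-35/36-39, exactly as in Protocol Table 9. Table 10 also reproduces. (SAP Table 7 prints 23-36 for the fourth column; the calculation supports the protocol's 23-26.)

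**Step 2: thresholds, 20% rule.**
- Pooled, n = 68: r = 16 gives Beta(16.5, 52.5), probability 0.771; r = 17 gives Beta(17.5, 51.5), probability 0.849. Threshold 17.
- 152 mg alone, n = 30: r = 7 gives Beta(7.5, 23.5), probability 0.689; r = 8 gives Beta(8.5, 22.5), probability 0.822. Threshold 8.

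With no events among the other 38, the pooled rule needs 17/30 = 57% at 152 mg; the 152 mg rule needs 8/30 = 27%.

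The same method gives 9 of 68 against 5 of 30 for the 10% rule, and 4 of 68 against 2 of 30 for the 3% rule.

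**Step 3: chance of a hold.** This was simulated with a look after each participant, in the order Part 1, Dose level 1, Dose level 2, Part 2B. Pooled holds are counted only once the 152 mg group has started.

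| Rule | Assumed rate, other 38 | Assumed rate, 152 mg | Pooled | 152 mg alone |
|---|---|---|---|---|
| 20% | 5% | 30% | 4% | 82% |
| 20% | 5% | 40% | 22% | 98% |
| 10% | 1% | 20% | 18% | 88-89% |
| 3% | 0% | 10% | 50% | 82% |

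Varying the rate in the other 38 from 0 to 5%, the pooled 20% rule fires in 0.3-4% of trials at a true 152 mg rate of 30%, 6-23% at 40% and 32-59% at 50%.

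**Step 4: reported Part 2A sizes.** Protocol 4.1 reports 12 and 11 treated. With the planned 30 and 22, the total is 30 + 12 + 11 + 22 = 75, of whom 11 + 22 = 33 are at 152 mg. Thresholds become 18 of 75 and 9 of 33. The first scenario gives 4% against 84%, so the result does not depend on the planned counts.

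**Step 5: cost of a 152 mg-only look.** Under the 20% rule it crosses in about 5% of trials at a true rate of 10% and 41-42% at exactly 20%. Under the 10% rule it crosses in 44% at exactly 10%.

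**The case against.** A reader might infer that Part 2B has no trigger able to detect excess toxicity. The documents do not support that, for three reasons.
- Protocol 9.4.1 adds absolute Grade 5 counts, which pooling does not dilute. The chance of at least 2 events in 30 is 0.45 at a 5% fatal related rate and 0.82 at 10%.
- An event at 152 mg after Day 28 still counts, because evaluability with an event has no time limit. The early clock makes event-free status provisional; it does not discard later events. Its separate effect was not quantified.
- The pooled neuropathy and GBS rules still respond to large excesses. With 0-5% elsewhere, the neuropathy rule fires in 58-79% of trials at a true 30%. With 0-1% elsewhere, the GBS rule fires in 93-94% at a true 20%.

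A second tempting step is to apply the 82% to everyone given either higher dose. It belongs to the 152 mg group alone. Adding the 116 mg cohort at the lower rate brings the first scenario to about 59% and the neuropathy scenario to about 74% (49% and 68% with the reported Part 2A sizes).

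Other points against the concern have weight. Part 2B followed DLT review of both dose levels, with 1 DLT among 7 evaluable at 152 mg. Internal safety review is ongoing. Protocol 4.3.2 expects exposure (AUC) at 152 mg every two weeks to resemble 76 mg weekly, although Protocol 2.3.1 predicts up to a two-fold higher peak, so a jump from 5% to 30% is illustrative. Part 1 is not purely 76 mg, since responders may switch to 152 mg every four weeks. Finally, the stated action is an enrollment hold, and enrollment is complete. What survives is the missing dose-specific trigger in Part 2B and the insensitivity of the pooled 20% rule.

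**Conclusion.** The point holds for non-fatal toxicity arising from Cycle 2 at 152 mg, chiefly Grade 4 related non-hematologic events. There the pooled rule has roughly a 4% chance of a hold where the same rule on the 152 mg group has 82%. The loss is smaller for neuropathy and GBS, absent for the Grade 5 counts, and no reason to stop pooling Cycle 1 CRS and ICANS.

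The thresholds follow exactly from the plan's prior and cut-off. The probabilities rest on assumed event rates, independent participants, a look after each one, and the stated enrollment order.

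With enrollment complete, the practical weight falls on interpretation. Under Protocol 9.4.1, meeting a criterion still prompts benefit/risk judgement for participants on treatment and notification of investigators, ethics committees and authorities. The absence of a hold says little about non-fatal toxicity specific to 152 mg.

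**What to change.** 1. Reconcile the evaluability clock in Protocol 9.4.1 and SAP 7.2.1 with the DLT window in Protocol 4.3.3, and state the pooling in both documents.
2. Keep the pooled rule. Have the existing safety review team also compute the plan's own posterior probabilities (same prior, 0.80 cut-off, limits and minimum counts) by dose level. Count the 152 mg group (Part 2A Dose level 2 plus Part 2B) from the first 152 mg dose. SAP 5.2 already defines this group, 152 mg being the RP2D. Show Part 1 switchers separately.
3. State the operating characteristics, including the crossing rates in Step 5. Table 9 covers a group of up to 39; extend it if a larger group is used (11 events at 40-43, 12 at 44-48).
4. Correct the 23-36 column in SAP Table 7.

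The cost is about a paragraph in each document, with no new data or committee. The downside is more frequent crossings when the true rate lies near a limit. The result feeds the existing benefit/risk review and the reporting of safety at 152 mg; no new treatment-stopping rule is proposed.

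### The third row of Protocol Table 9 counts Grade 4 events only, so swapping the last Grade 4 participant for one related non-hematologic death can remove the hold

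*Protocol*

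**What the plan says.** Protocol 9.4.1 lists the events that the sponsor monitors and the counts that force a temporary hold. For non-hematologic toxicity the list, the rule text and Table 9 all use Grade 4. The list entry is "Grade 4 treatment-related non-hematologic events (excluding CRS and ICANS"). The text reads "Separate but similar criteria will be used for participants with Grade 3-4 ICANS and treatment-related Grade 4 non-hematologic events (excluding CRS and ICANS"), and the third row of Table 9 gives the "Minimum number of participants with Grade 4 treatment-related non-hematologic events (excluding CRS and ICANS) that would lead to a temporary enrollment hold". The rule is a Beta(0.5, 0.5) prior, a 20% reference rate, a posterior probability of at least 0.80, and a floor of 4 events. SAP 7.2.1 and its Table 7 define the event in the same way.

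Deaths are handled by separate criteria after Table 10. One CRS death or one ICANS death is enough, and so is "1 Grade 5 treatment-related peripheral neuropathy or IR neurologic event". For the rest the criterion is "Any 2 treatment-related Grade 5 events (excluding CRS and ICANS and peripheral neuropathy/IR neurologic event"). Protocol Appendix 3 defines Grade 5 as a grade distinct from Grade 4. Neither document adds a Grade 5 event to the third-row count.

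**The concern.** A toxicity boundary should not become more lenient when an outcome gets worse. Here it can. Take a trial one Grade 4 participant short of the third-row threshold. If the next participant has a related Grade 4 non-hematologic event, the hold is mandatory. If that participant instead dies of a related non-hematologic cause outside CRS, ICANS and neurologic toxicity, and was never recorded at Grade 4, the row stays one short and the death rule stands at one of two.

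The hold stops enrollment, and it does two further things. Under Protocol 9.4.1, "Participants who have already started study intervention may continue treatment only if the benefit/risk assessment for the participant is judged to be positive", and written notice goes to investigators, ethics committees, regulators and any CROs. In the state described, none of this is compelled by a pre-specified count.

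**Working it through.** **1. Reproduce the table.** With x participants with events among n evaluable, the posterior is Beta(0.5 + x, 0.5 + n − x). The threshold t(n) is the smallest x with Pr(rate > 20%) ≥ 0.80, and at least 4. For every n from 10 to 39 this gives the printed 4, 5, 6, 7, 8, 9, 10. For n of 40 or more, which the footnote leaves to calculation, it gives 14 at n = 53, 18 at n = 75 and 19 at n = 76. Every band of Table 10 also reproduces. The thresholds are not in question.

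**2. Evaluate the gap.** Compare t − 1 Grade 4 participants (as written, death ignored) with t − 1 plus the one death (Grade 5 counted):

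| n | As written | Pr(rate > 20%) | Death counted | Pr(rate > 20%) |
|---|---|---|---|---|
| 10 | 3 | 0.795 | 4 | 0.934 |
| 13 | 3 | 0.634 | 4 | 0.837 |
| 30 | 7 | 0.689 | 8 | 0.822 |
| 53 | 13 | 0.798 | 14 | 0.877 |
| 76 | 18 | 0.792 | 19 | 0.861 |

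In each row the death carries the posterior across the plan's own 0.80 line, yet the written rule does not see it.

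**3. List what closes the gap.** No hold follows only if all of these are true:
- there is exactly one such death;
- it is related and non-hematologic, and not from CRS, ICANS or neurologic toxicity;
- the participant was never recorded at Grade 4;
- the Grade 4 count is exactly one short;
- no other criterion is met.

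The last condition matters because the third row excludes only CRS and ICANS. Neurologic Grade 4 events count there and also in Table 10, whose neurologic threshold is 2 participants at 6-11 evaluable and 3 at 12-19. Its footnote goes further: "if there are 2 participants experiencing the identified AE out of the first 4 evaluable participants, the study will be put on hold".

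The denominator matters too. A participant without an event is evaluable only among "those without such an event who have been followed for at least 28 days from first dose". The 18+1 of 76 example takes the deceased participant as evaluable, which is right for a death at day 28 or later. If an earlier death left the denominator, 18 of 75 would reach the threshold of 18.

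**4. How often it matters.** The documents give no event rates, so these are assumptions. Each participant independently has a counted Grade 4 event (probability a), a related death of the relevant kind (probability b), or neither. With G and D the running totals:
- written rule: hold when G ≥ t(n) or D ≥ 2;
- changed rule: hold when G + D ≥ t(n) or D ≥ 2.

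An exact forward recursion over 76 participants gives the table below. 'Earlier' means that the changed rule fires strictly first, as a share of all trials.

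| a / b | Hold, written | Hold, changed | Earlier, any n | Earlier, n ≥ 53 | Earlier, n ≥ 75 |
|---|---|---|---|---|---|
| 25% / 3% | 94.8% | 96.0% | 30.2% | 1.7% | 0.10% |
| 20% / 2% | 74.9% | 77.9% | 20.5% | 2.0% | 0.14% |
| 15% / 2% | 57.7% | 60.0% | 11.4% | 0.6% | 0.04% |
| 10% / 1% | 22.0% | 23.0% | 2.2% | 0.02% | <0.01% |
| 5% / 1% | 18.0% | 18.1% | 0.3% | <0.01% | <0.01% |

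These are upper bounds, because every death is treated as newly counted. If half the deaths are hematologic or already counted at Grade 4, the any-n shares fall to 15.1%, 10.3%, 5.7%, 1.1% and 0.15%. If no death is newly counted, the effect is zero. Adding Table 10 with a quarter of Grade 4 events assumed neurologic lowers the two largest upper bounds to 27.0% and 18.5%.

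**5. Where the trial stands.** Protocol 4.1 reports enrollment complete, with 12 + 11 = 23 treated in Part 2A. Adding the planned 30 in Part 1 gives 53, and the planned 22 in Part 2B gives about 75. The last columns are therefore the relevant ones.

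**The case against.** The best defense is that this is a deliberate structure. Protocol and SAP agree. Deaths are weighted far more heavily than Grade 4 events: one or two deaths against 4 to 19 participants. Any pair of separate tallies leaves a state in which each is one short. This stands in part: there is no inconsistency, and a second related death triggers a hold at any n. It does not explain why the worse of two outcomes should be the one that leaves the hold untriggered, and no rationale is given.

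A second defense is that a single related death already gets attention. Serious events are reported within 24 hours (Protocol 8.3.1.1), and the sponsor must notify regulators, ethics committees and investigators as local rules require (8.3.4). Grade 4 non-hematologic toxicity ends treatment (Table 6), safety issues go to the sponsor at once (Section 8), an internal team reviews cumulative data, and the sponsor may stop at any time (10.1.9). This covers much of the ground, but none of it sets a count at which the hold becomes mandatory, and the study has no DMC.

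A reader might also infer that the plan leaves open whether a Grade 4 event that turns fatal stays in the count. The documents do not support that as a serious ambiguity. Protocol 9.4.1 counts participants observed to have the event, and someone recorded at Grade 4 who later dies was so observed. An explicit sentence would still help.

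**Conclusion.** The point holds as a minor ordering flaw in the event definition, confined to the one state set out above.

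Three stronger readings are not supported. The Table 9 thresholds are not wrong; all reproduce. The plan does not ignore deaths; one CRS, ICANS or related neurologic death, or any two other related deaths, force a hold. And the 30.2% figure is not the present effect. It accumulates from the first participant under the highest assumed rates with every death newly counted, and most of it arises at sample sizes already passed.

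From the 53rd participant on, the earlier-hold share is at most about 2% of trials, and from the 75th at most 0.14%. All shares rest on the assumed rates and on events occurring in participant order, so late events in continuing participants are not modelled. With enrollment complete, what remains is the benefit/risk check on those still treated and the hold notifications. The practical effect is near zero, and the value lies mainly in a rule that ranks outcomes correctly.

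**What to change.** In Protocol 9.4.1 and SAP 7.2.1, change the grade in this event definition from Grade 4 to Grade 4 or 5 and keep the rest of the definition. Each document needs it in three places: the monitored list, the rule text and the third row of Table 9 or Table 7. Add that each participant counts once, so a Grade 4 event that becomes fatal stays one count. Keep every threshold and all the separate Grade 5 criteria.

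The cost is a few words in six places and an occasional slightly earlier hold after one related non-hematologic death. No threshold has to be recalculated.
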